The participant's ongoing treatments (concomitant medications including any anti-influenza and anti-pneumococci vaccinations) will be reviewed and updated as necessary both for COPD and CV comorbidities, particularly HF, IHD and/or AF. Details of all concomitant medications will be recorded. Doses of all COPD medications can be adjusted by the clinical investigator according to licenced dosages for COPD for each inhaled drug, at any time during the study.

Participants will be questioned about the occurrence of any adverse events and details will be recorded on the eCRF.

Prescriptions for further supplies of the study medication, for collection from the local pharmacy or hospital pharmacy department, will be issued. Prescription data will be captured on the eCRF.

Visit 6: End of Study after 12 months of treatment or early withdrawal

Participants will be asked to complete the CAT and mMRC questionnaires.

Spirometry will be performed in accordance with ATS and ERS guidelines (Miller et al 2005). The spirometry test will be performed before and 30 minutes after bronchodilation (4 inhalations of 100 µg salbutamol).

Vital signs, including blood pressure and heart rate, will be measured. A 12-lead ECG will also be performed.

Medical history and history of COPD and CV disease will be reviewed and updated as necessary.

Participants will be asked to bring back all the unused medication and the empty drug devices and they will also be asked about their compliance with the study procedures and treatment.

Information about any hospitalizations or any unexpected medical events, particularly moderate exacerbations treated with antibiotics and/or steroids will be collected. Information will be obtained by reviewing the patient's medical records and prescribed medication and also from direct questioning of the participant.

Participants will be questioned about the occurrence of any adverse events and details will be recorded on the eCRF.

For participants who are withdrawn before the end of the study the reason for early withdrawal will be recorded on the eCRF.

Participants who complete the 12 month randomized treatment period will continue to be prescribed the most appropriate treatment for their condition at the discretion of the investigator. Doses of all COPD medications can be adjusted by the clinical investigator according to licenced dosages for COPD for each inhaled drug, at any time during the study.

Visit 7: Follow-up 3 months after End of Study

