All the other counting variables will be analysed with the same model.

All the continuous variables will be summarized at each visit by means of descriptive statistics. Mean change from baseline value and the 95% confidence intervals will be calculated. P-values of paired t-tests will be provided for mean changes from baseline.

Change in continuous variables will also be analysed using an ANCOVA model, with treatment group, centre and age as factors and baseline as covariate.

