3.2 Visit Schedule and Visit Windows

Assessments and study visits will be performed as listed in the table below:

Procedure	Screening (up to 10 days before Day 1)	Intervention Period [months]					Follow-up (3 months after last study treatment)
		day 1 (randomization)	3 months	6 months	9 months	12 months (or early withdrawal)	
Visit number	Visit 1	Visit 2	Visit 3	Visit 4	Visit 5	Visit 6	Visit 7
Informed consent	X						
Inclusion and exclusion criteria	X	X					
Spirometry*		X				X	
COPD assessment test (CAT)	X	X	X	X	X	X	X
mMRC dyspnea scale	X	X	X	X	X	X	X
Demography	X						
Physical examination including height and weight	X	X	X	X	X	X	X
Medical history (including substance usage)	X	X	X	X	X	X	X
History of COPD and cardiovascular disease (particularly HF, IHD or AF)	X	X	X	X	X	X	X
Past and current medical conditions	X						
Laboratory assessments	X						
12-lead ECG	X					X	
Chest x-ray	X (Optional)						
Vital signs (blood pressure and heart rate)	X	X	X	X	X	X	
Randomization		X					

 cros nt	Forms				
	Title	Statistical Analysis Plan Template			
	Code		Version	Effective Date	Page
	FRM_ST03_032		02	02 Oct 2017	9 of 26

Procedure	Screening (up to 10 days before Day 1)	Intervention Period [months]					Follow-up (3 months after last study treatment)
		day 1 (randomization)	3 months	6 months	9 months	12 months (or early withdrawal)	
Visit number	Visit 1	Visit 2	Visit 3	Visit 4	Visit 5	Visit 6	Visit 7
Study treatment checked and prescribed		X	X	X	X		
Assessment of symptoms and hospitalizations			X	X	X	X	X
Vaccination check		X	X	X	X		
Adverse event review		X	X	X	X	X	
Serious adverse event review		X	X	X	X	X	X
Concomitant medication review	X	X	X	X	X	X	X

CV = cardiovascular, HF = heart failure, IHD = ischemic heart disease, AF = atrial fibrillation, CAT = COPD Assessment Test, mMRC = modified Medical Research Council.

* Participants with a diagnosis of COPD confirmed by spirometry within the last 3 years, will be immediately eligible for the study after hospital discharge. Participants without a previous spirometric confirmation must have a spirometry test, which must be performed at least 8 weeks after discharge. If confirmed then they can be recruited to the study.

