**Participants will be contacted by telephone each month, by the clinical investigator or by a research staff member, to check compliance with the study procedures, vaccination and treatment. Information about any hospitalizations or any unexpected medical events, particularly moderate exacerbations treated with antibiotics and/or steroids will be collected

Paragraph no. 8 “Study Assessments and Procedures” of Study Protocol contains additional details about scheduled visits and time windows.

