Patients who died will be presented with a breakdown of the causes of death (Cardiovascular death/Other) by treatment and overall.

QoL variation (change in CAT total score from baseline to end of treatment period)

CAT total score, the change from baseline will be summarised by treatment at each visit by means of descriptive statistics. 95% CIs for the mean change will also be calculated.

Forms			
Title	Statistical Analysis Plan Template		
Code	Version	Effective Date	Page
FRM_ST03_032	02	02 Oct 2017	22 of 26

A comparison between treatment groups will be performed with an ANCOVA model with the change from baseline of the CAT total score to the end of treatment period (i.e. Visit 6) as dependent variable, treatment group and centre as qualitative independent variables and age and baseline value of the variable as quantitative independent variables.

The number of patients and the number of patients considered in the model will be provided by treatment. P-values of the independent variables will also be presented.

The adjusted means for treatments and the relative 95% CIs will be presented. The difference between the adjusted means for LABD and LABD + ICS will be calculated with the relative 95% CI and p-value.

The following SAS® code will be used to estimate the ANCOVA model:

```
proc mixed data = dataset;
class TMT CENTER;
model CHG = TMT CENTER AGE BASELINE;
lsmeans TMT / cl;
lsestimate 'LABD vs LABD + ICS' TMT 1 -1 / cl;
run;
```

where CHG represents the change from baseline of the CAT total score at Visit 6, TMT the treatment group, CENTER the center, AGE the age and BASELINE the baseline value of the variable.

The variable TMT will be ordered in SAS in the following order:

- 1 = LABD;
- 2 = LABD + ICS.

Change in mMRC dyspnea score from baseline to end of treatment period

The same analyses described for the change in CAT total score will be performed for the change in mMRC dyspnea score.

Change in FEV1 from baseline to the end of treatment period

The same analyses described for the change in CAT total score will be performed for the change in FEV1.

Change in FVC from baseline to the end of treatment period

The same analyses described for the change in CAT total score will be performed for the change in FVC.

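### CAT and mMRC are compared between arms only at Visit 6, with no rule for early-withdrawal or absent scores; if withdrawal depends on the score and differs by arm, these secondary contrasts can be biased

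*SAP*

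**What the plan says.** **Model.** In SAP 7.2 the between-group comparison of CAT is an ANCOVA with the "change from baseline of the CAT total score to the end of treatment period (i.e. Visit 6) as dependent variable". The note to the code repeats this: "where CHG represents the change from baseline of the CAT total score at Visit 6". The PROC MIXED call has treatment, centre, age and baseline, but no visit term and no REPEATED statement. For the dyspnoea scale, "The same analyses described for the change in CAT total score will be performed for the change in mMRC dyspnea score". Protocol 9.4.6 likewise names ANCOVA for continuous variables and no repeated-measures model.

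**Other visits.** The schedules (Protocol 1.3, SAP 3.2) collect CAT and mMRC at Visits 3, 4 and 5 as well. Their use is descriptive: "CAT total score, the change from baseline will be summarised by treatment at each visit by means of descriptive statistics", with 95% CIs for the mean change.

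**Visit 6.** Protocol section 8 titles it "Visit 6: End of Study after 12 months of treatment or early withdrawal". The SAP schedule gives the column the same double meaning (headed "12 months (or early withdrawal"). For windows, SAP 3.2 says that Protocol section 8 "contains additional details about scheduled visits and time windows", but that section has no rule separating a 12-month score from an early-withdrawal score.

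**Missing scores.** Protocol 9.4.4 leaves the handling to the SAP. SAP 4.7 points to chapters 5 to 8, and chapter 7 has no rule for a missing CAT or mMRC score, none for patients who die, and no sensitivity analysis for these endpoints. ITT (SAP 4.2.3) requires only one post-baseline efficacy evaluation, so a patient can be in ITT and have no Visit 6 score.

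**The concern.** A single-visit ANCOVA compares those patients who have that visit. If patients who are doing badly leave, and do so more in one arm, the remaining groups are no longer alike, and the model does not use the earlier scores that record the worsening.

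Such a pattern is plausible here. Treatment is open label. Under Protocol 7.1 a hospitalised patient stays in at the discretion of the investigator or the patient. The plan itself expects the composite of re-hospitalisation and death in 15% of the LABD arm and 9% of the LABD+ICS arm. Secondary p-values are read at 0.05 without adjustment (Protocol 9.4.5). At stake is whether a quality-of-life or dyspnoea difference, or its absence, reflects treatment or who stayed.

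**Working it through.** **The plan's own figures.** No SD, effect size or power is given for CAT or mMRC. The figures that bear on this point reproduce: 464/(1 − 0.10) = 515.6, so 516 per arm; 10% of 516 is about 52 patients lost per arm. For the primary endpoint, HR = ln(0.91)/ln(0.85) = 0.580 and 464 × (0.15 + 0.09) = 111 events give 80.0% power by Freedman's formula. The 10% is not split by arm or linked to outcome.

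**Assumptions for the simulation (not from the documents).** 516 per arm; five visits (2 to 6); CAT mean 20, SD 7; correlation 0.7 between adjacent visits, falling as 0.7^lag; a true difference (LABD+ICS minus LABD) growing linearly to −1 or 0 at Visit 6. After each of Visits 2 to 5 a patient leaves with logit(p) = a + b × (score − 20)/7. Here b = 0 is random loss and b = 1 means worse scores leave; a sets the amount. Half of those who leave after a post-baseline visit supply an early-withdrawal score, taken as their last attended value. There were 300 runs per scenario.

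**Check on the set-up.** Baseline to Visit 6 correlation is 0.7^4 = 0.24; residual SD is 7 × √(1 − 0.24²) = 6.80; SE is 6.80 × √(2/516) = 0.42. The simulated full-data SE is 0.40 to 0.44.

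**Mean estimated difference**

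| Scenario | Loss, LABD / LABD+ICS | Full data | Completers only | Early-withdrawal scores counted as Visit 6 | All visits used |
|---|---|---|---|---|---|
| A. Random, true −1 | 10% / 10% | −1.01 | −1.01 | −0.99 | −1.02 |
| B. Score-dependent, same in both arms, true −1 | 10% / 9% | −0.99 | −0.98 | −0.98 | −0.99 |
| C. Score-dependent, true −1 | 15% / 9% | −0.99 | −0.86 | −0.98 | −0.98 |
| D. As C, true 0 | 14% / 9% | 0.02 | 0.13 | 0.01 | 0.02 |
| E. Score-dependent, true 0 | 25% / 15% | 0.00 | 0.21 | −0.04 | −0.01 |
| F. Opposite mechanisms (b = 1 v −1), true 0 | 10% / 10% | 0.01 | 0.41 | −0.06 | 0.00 |
| G. As C, plus 2-point worsening over time | 16% / 9% | −1.01 | −0.87 | −0.99 | −1.01 |

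The Monte Carlo error of one mean is about 0.45/√300 = 0.03. Columns share the same simulated patients, so differences between them are more precise. The completers' SE is 0.42 to 0.47. The last column is an arm-specific sequential regression on all visits, which stands in for a repeated-measures likelihood.

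**In terms of error rate.** For the completers' ANCOVA with no true difference, bias/SE is 0.13/0.46 = 0.29 (D), 0.21/0.47 = 0.45 (E) and 0.41/0.45 = 0.90 (F). By the normal approximation, the false-positive rate is about 6%, 7% and 15% instead of 5%.

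**A harsher case.** With 464 per arm, SD 7, no true difference, 150 runs, and worsening driving withdrawal in one arm only (27% v 5% missing at 12 months), the bias was:
- 0.49 points for completers (SE 0.336, 28.7% rejection);
- 0.31 with early-withdrawal scores counted as Visit 6 (SE 0.300, 18.0%);
- 0.00 with a repeated-measures model (SE 0.329, 6.7%).

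With equal random 9% loss, all three gave −0.01, with SEs of 0.321, 0.301 and 0.316. So the repeated-measures model costs no precision relative to completers.

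**The case against.** A reader might infer that the CAT result is biased by design. The documents do not support that: they give one overall dropout figure, and where the same mechanism acts in both arms the bias is nil even if it depends on the score (A, B). The 27% v 5% case averages 16% loss against a planned 10% and is a stress test. The 15% v 9% split matches the expected event rates, but no document says that an event means withdrawal; Protocol 7.1 lets patients stay after hospitalisation and change regimen.

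A reader might also infer that counting early-withdrawal scores as 12-month scores is the source of the bias. The SAP never states such a rule; it follows only from the shared visit label. In both simulations, including those scores reduced the bias: to within about 0.06 of the full-data value in A to G, and from 0.49 to 0.31 in the harsher case. How far it helps depends on how many supply a score and when, so the missing rule still matters.

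Nor are Visits 3 to 5 thrown away: they are tabulated by arm with CIs, and the number of patients in the model is reported by arm. SAP 4.7 sends critical missing data to data review. These steps make a problem visible but do not adjust the contrast, and a decision at data review in an open-label trial is not a pre-specified rule.

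Finally, the good showing of the all-visits analysis is partly built in. Withdrawal in these simulations depended on recorded scores, so missing at random held. Withdrawal driven by unrecorded worsening, and death, were not tested. That stands.

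**Conclusion.** The gap is real: one visit carries the whole between-group comparison of CAT and mMRC, that visit has two meanings, and nothing says what happens when it is absent. The consequence is a risk, not an established bias. With CAT SD 7 and the assumed correlations, the completers' bias is about 0 with similar loss in both arms, 0.1 to 0.2 points with loss of 15% v 9% to 25% v 15%, and 0.4 to 0.5 in extreme cases. It arises mainly from patients with no Visit 6 score. In C and G it shrank a true benefit of 1 point to about 0.87; the direction in the real trial cannot be derived from the documents. mMRC was not simulated, so for it the argument is structural only.

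The point does not extend to a change for FEV1 and FVC. They are measured only at Visits 2 and 6, so there are no intermediate values to use, and excluding early-withdrawal tests would create the completers-only analysis that performed worst above. These are secondary endpoints; the primary time-to-event result is unaffected.

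**What to change.** For CAT and mMRC:

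1. Make the main comparison a mixed model for repeated measures on Visits 3 to 6, with treatment by visit, baseline by visit, centre, age and unstructured covariance. Report the 12-month contrast.
2. Assign each early-withdrawal score to a visit by its actual date. If that visit already has a scheduled assessment, keep the scheduled one. Define the windows so that a score in the first weeks after randomisation also has a place.
3. Keep the planned Visit 6 ANCOVA as a sensitivity analysis.
4. State that scores after death are not defined, and show deaths by arm beside the CAT and mMRC results. SAP 7.2 already tabulates deaths by treatment.
5. List the change in SAP 4.8, because Protocol 9.4.6 specifies ANCOVA.

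**Cost.** No new data; a SAP revision, a documented departure from the protocol analysis and a few lines of code. The model assumes missing at random and does not resolve death. Under the tie rule some early-withdrawal scores (for example at month 4, when Visit 3 is already filled) leave the main model, though they remain in the ANCOVA. A further sensitivity analysis for scores not missing at random would address what the model cannot.

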7.3 Analysis of exploratory efficacy endpoints

Not foreseen.

7.4 Evaluation of pharmacodynamics

Not foreseen.

Forms			
Title	Statistical Analysis Plan Template		
Code	Version	Effective Date	Page
FRM_ST03_032	02	02 Oct 2017	23 of 26

8. Evaluation of Safety

8.1 Adverse events

Definitions and data conventions

Pre-treatment adverse events

An AE will be classified as pre-treatment AE if it starts before the date of randomization (AE onset date < date of randomization).

Treatment-emergent adverse event (TEAE)

An AE will be classified as a TEAE if it starts on or after the date of randomization (AE onset date \geq date of randomization).

In case of missing or incomplete dates not allowing a direct allocation to any of the two categories of AEs, a worst-case allocation will be done according to the available parts of the onset and the end dates. The AE will be allocated to the first category allowed by the available data, according to the following order:

- TEAE
- Pre-treatment.

Serious adverse event (SAE)

A SAE is an AE judged as serious.

Adverse drug reaction (ADR)

An ADR is an AE with relationship to study treatment equal to “Yes”.

Severe adverse event (SAE)

A SAE is an AE judged as severe intensity.

Adverse event leading to study withdrawal

An AE leading to study withdrawal is an AE with action taken equal to “Drug withdrawn” or “Drug interrupted”.

Count of adverse events

Two AEs with the same Preferred Term (PT) and classified in the same category (pre-treatment AE or TEAE) will be considered as two different events when calculating the “number of events” in the tables.

Statistical analysis

Pre-treatment AEs and TEAEs will be presented separately. Pre-treatment AEs will be presented in the listings only.

The number of treatment-emergent AEs, SAEs, ADRs, severe AEs and AEs leading to discontinuation, and the number and the percentage of patients experiencing treatment-emergent AEs, SAEs, ADRs, severe AEs and AEs leading to discontinuation will be summarised by treatment group. Differences between groups will be evaluated using Chi-square test or Fisher’s exact test (if more than 20% of the cells in a contingency table have expected counts less than 5).

Title	Statistical Analysis Plan Template		
-------	------------------------------------	--	--

Code	Version	Effective Date	Page
FRM_ST03_032	02	02 Oct 2017	24 of 26

AEs will be coded using the MedDRA dictionary (version 21.0). The SOCs and PTs will be used for tabulation. The number of treatment-emergent AEs and the number and the percentage of patients with at least one treatment-emergent AE will also be presented by SOC and PT by treatment group.

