7.1. Discontinuation of Study Intervention

Participants who are hospitalized during the study period will be allowed to continue in the study until the end at the discretion of the principal investigator and/or the participant. The investigator/participant can decide to discontinue the study drug for safety or efficacy reasons.

Albeit we will invite patients and doctors to stick to the initial treatment unless required by changed medical condition, the specific COPD treatment regimen (LABD(s) without ICS or LABD(s) + ICS) can be changed at any point during the study. Treatment with ICS in the only LABDs group will be permitted if, on clinical Investigators judgement, it would be necessary for patient temporary conditions for at maximum 15 days in case of patient treated at home or for 15 days (at maximum) after hospital discharge in case of hospitalised patient. If the ICS treatment will surpass these periods, the patient will be considered being switched to the LABD + ICS group and considered as protocol violator.

See the SoA for data to be collected at the time of intervention discontinuation and follow-up and for any further evaluations that need to be completed.

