9.4.7. Safety Analyses

The number and the percentage of patients experiencing adverse events, adverse drug reactions, serious adverse events, severe adverse events and adverse events leading to study withdrawal will

be summarized by treatment group. Adverse events will also be summarized by System Organ Class (SOC) and Preferred Term (PT) using the Medical Dictionary for Regulatory Activities (MedDRA) dictionary and comparison between treatments will be performed using a Chi-square test or Fisher's exact test, as appropriate.

Any other safety variables to be summarized by treatment group using descriptive statistics will be detailed in the SAP.

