4.1 General

Descriptive statistics will be provided for all variables in the summary tables for the treatment according to the type of variable summarized.

Forms			
Title	Statistical Analysis Plan Template		
Code	Version	Effective Date	Page
FRM_ST03_032	02	02 Oct 2017	11 of 26

Quantitative variables will be summarised by using n, arithmetic mean, SD, median, minimum and maximum.

Categorical variables will be summarised by using frequency distributions and percentages.

Hypothesis testing will be carried out at the alpha = 0.05 level (two-sided) when comparing treatments. For all inferential analyses, p-value will be rounded to three decimal places. Statistical significance will be declared if the rounded p-value will be less than or equal to 0.05.

All data collected in the CRF will be presented in the listings.

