5.3 Study discontinuations

Definitions and data conventions

Date of completion/discontinuation

Date of study completion will be the date of study end recorded in the study conclusion/withdrawal form.

If the date of study completion is missing, the date of last study visit performed (i.e. Date of Visit 6) will be used.

Forms			
Title	Statistical Analysis Plan Template		
Code	Version	Effective Date	Page
FRM_ST03_032	02	02 Oct 2017	14 of 26

Date of discontinuation will be the date of withdrawal recorded in the study conclusion/withdrawal form.

Statistical analysis

Randomised patients who completed the study will be presented by treatment and overall for the Randomised population. Randomised patients who discontinued from the study prematurely will also be presented with a breakdown of the reasons for discontinuation by treatment and overall for the Randomised population.

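### SAP 8.1 defines AEs leading to study withdrawal by drug action alone and tabulates them under a second, undefined label, so the row does not deliver the category planned in Protocol 9.4.7

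*SAP*

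**What the plan says.** Protocol 9.4.7 lists, among the AE categories to be summarised by arm, "adverse events leading to study withdrawal".

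SAP 8.1 defines the category this way: "An AE leading to study withdrawal is an AE with action taken equal to" either drug withdrawn or drug interrupted. No condition on study status follows.

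The analysis paragraph of SAP 8.1 uses a different name. The quantities summarised by treatment group, as events and as patients with percentages, are "The number of treatment-emergent AEs, SAEs, ADRs, severe AEs and AEs leading to discontinuation". That last term has no definition in the SAP. On the comparison between arms it says "Differences between groups will be evaluated using Chi-square test or Fisher’s exact test", and SAP 4.1 sets the level: "Hypothesis testing will be carried out at the alpha = 0.05 level (two-sided) when comparing treatments".

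Stopping the drug and leaving the study have separate sections in the protocol. Section 7.1 concerns the drug: "The investigator/participant can decide to discontinue the study drug for safety or efficacy reasons". Section 7.2 concerns withdrawal from the study. For leaving the study, SAP 5.3 has its own source: "Date of discontinuation will be the date of withdrawal recorded in the study conclusion/withdrawal form". It also tabulates the reasons for discontinuation by arm.

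SAP 4.8, which lists changes from the protocol's planned analyses, does not mention this definition.

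**The concern.** The definition carries the label of one event (the patient leaves the study because of an AE) and the content of another (something was done with the drug because of an AE). In a pragmatic trial these can come apart. Protocol 7.1 lets hospitalised patients continue in the study and lets the regimen change at any time. Protocol 9.4.6 and SAP 7.1 expect some patients to add or stop ICS, and the primary analysis does not censor them at that switch. A patient who stops or interrupts an inhaled drug because of an AE and stays under follow-up meets the SAP definition without having withdrawn.

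At stake is one line of the AE overview table and its p-value. A reader would take it as a measure of tolerability severe enough to end participation. As defined, it is a mixture whose components have different clinical meanings, under a name that the SAP does not define.

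**Working it through.** No figure in the plan depends on this definition, so there is nothing to reproduce. The check sets the rule against the protocol category, patient type by patient type.

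| Patient with an AE | Counted by SAP 8.1 rule | Belongs in Protocol 9.4.7 category |
|---|---|---|
| (a) Drug interrupted, stays in study | Yes | No |
| (b) Drug withdrawn, stays in study | Yes | No |
| (c) Drug withdrawn or interrupted, leaves study because of the AE | Yes | Yes |
| (d) Other action recorded, leaves study because of the AE | No | Yes |

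The rule counts a + b + c. The protocol category is c + d. The net error is therefore

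(a + b + c) − (c + d) = a + b − d.

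The documents give no value for a, b or d, so neither the sign nor the size of this difference is known.

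An illustration with assumed rates shows how open it is. The only documented input is 516 randomised per group (Protocol 9.2, SAP 3.3), used as an approximate denominator. Assume that the true rate of study withdrawal for an AE is c + d = 3% per arm, which is 516 × 0.03 = 15.5 patients.

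- a + b = 2%, d = 0: the row shows 3% + 2% = 5%, or 516 × 0.05 = 25.8 patients. The ratio to the true rate is 5/3 = 1.7.
- a + b = 6%, d = 0: the row shows 3% + 6% = 9%, or 516 × 0.09 = 46.4 patients. The ratio is 9/3 = 3.0.
- a + b = 2%, d = 3% (the extreme in which every true withdrawal carries another action code): the row shows 3% + 2% − 3% = 2%, or 516 × 0.02 = 10.3 patients. The ratio is 2/3 = 0.67.

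So the row can stand above or below the true figure, depending wholly on assumptions.

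Two further checks bound the effect:

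1. **Efficacy.** Censoring in SAP 7.1 uses the date of Visit 6 or of withdrawal, and time on study in SAP 7.2 uses the date of completion or withdrawal. Neither calls on the AE definition.
2. **Availability of the right data.** Protocol 8.3.4 requires a study withdrawal caused by an AE to be recorded in the CRF with its reason, and SAP 5.3 already breaks down discontinuation reasons. The information needed for a patient count is collected.

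**The case against.** Several points on the other side are fair.

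- **The output label.** The tested row is called AEs leading to discontinuation, not study withdrawal. An AE that stopped the drug fits that label. This stands in part: for drug withdrawn, the fault is that heading and output label differ. It does not explain why interruption is included, nor does it deliver the category that the protocol named.
- **The meaning of interrupted.** Neither document defines it, and the eCRF options are not shown. That it means a temporary stop is an inference from its being listed beside withdrawn. It is the plain reading, but it should be confirmed.
- **Looseness in the protocol.** In Protocol 8.3.4 a subheading on treatment discontinuation introduces text about subjects withdrawn from the study. Protocol 9.4.6 equates withdrawal during treatment with the date of discontinuation. The Schedule of Activities has only an early-withdrawal column. This explains how the SAP wording arose, but sections 7.1 and 7.2 remain distinct.
- **The correct quantity is not lost.** SAP 5.3 reports reasons for study discontinuation, and SAP 4.1 lists all CRF data. This stands and limits the consequence.

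A reader might infer more than the documents support. One inference is that the row overstates withdrawals by a known multiple. That needs assumed rates and sets the missed patients, type (d), to zero. Another is that disagreement with the disposition table would prove the error. That table uses the Randomised population, while AE analyses use the Safety population by treatment received, so exact agreement is not assured even under a sound definition. A third is that the LABD+ICS arm would be inflated more because only it starts with ICS to stop. That is possible, but nothing in the documents sizes it.

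**Conclusion.** The point holds as a defect of definition and labelling. Followed as written, SAP 8.1 puts patients who stayed in the study into the category that stands in for study withdrawals, can leave out some who did withdraw, and tests the result between arms under an undefined name. Reading interruption as temporary rests on plain wording, and the net error (a + b − d) could have either sign.

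The effect is confined to one AE summary category and its test. SAP 3.6 names AEs as the safety endpoint, not this category, and no powered safety comparison is planned. The point is worth correcting because it costs little, not because any main conclusion of the trial depends on it.

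**What to change.** In SAP 8.1, replace the single definition with three, and use the same names in the analysis paragraph and tables:

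1. **AE leading to drug withdrawn:** action taken is drug withdrawn. Report events and patients.
2. **AE leading to drug interrupted:** action taken is drug interrupted. Report events and patients.
3. **Study withdrawal due to an AE:** the reason on the study conclusion/withdrawal form is an adverse event. Report patients. Add an event count only if the form links to the AE record, which the documents do not show.

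Drop the undefined term, AEs leading to discontinuation. If between-arm tests are kept, test each row separately. Confirm from the eCRF completion guide what the interrupted code means.

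The cost is SAP wording and two extra table rows, using data already collected. If the SAP is not reissued, its Introduction already provides for explaining deviations in the clinical study report.
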